2. RATIONALE	
3. THEORETICAL FRAMEWORK	
4. RESEARCH QUESTION/AIM(S)	
5. STUDY DESIGN/METHODS	
6. STUDY SETTING	
7. SAMPLE AND RECRUITMENT	
8. ETHICAL AND REGULATORY COMPLIANCE	
9. DISSEMINATION POLICY	
10. REFERENCES	
11. APPENDICES	

KEY STUDY CONTACTS

Chief Investigator	[name] Clinical Research Fellow Clinical Investigation and Research Unit Royal Sussex County Hospital [name] [contact] E-mail: [contact]
Study Co-ordinator	[name] Clinical Research Fellow Clinical Investigation and Research Unit Royal Sussex County Hospital [name] [contact] E-mail: [contact]
Sponsor	[name] Head of Research and Development Brighton and Sussex University Hospitals NHS Trust Research and Development Office [name] [contact] E-mail: [contact]
Joint-sponsor(s)/co-sponsor(s)	N/A
Funder(s)	Names and contact details of ALL organisations providing funding and/or support in kind for this study
Key Protocol Contributors	[name] Consultant Clinical Oncologist Sussex Cancer Centre [name] [contact] E-mail: [contact] [name] Consultant Clinical Oncologist The Royal Marsden Hospital [name]

	
[contact] E-mail: [contact]
 
[name] Professor of Clinical Oncology Institute of Cancer Sciences & Beatson West of Scotland Cancer Centre University of Glasgow [name] [contact] E-mail: [contact]
 
[name] The Walton Centre [name] [contact] E-mail: [contact]

--	--

STUDY SUMMARY

Study Title	B rain I maging to predict T oxicity in E lderly patients after R adiotherapy
Internal ref. no. (or short title)	BRITER study
Study Design	Observational cohort imaging study
Study Participants	Patients newly diagnosed with glioblastoma aged \geq 65 years undergoing radiotherapy treatment
Planned Size of Sample (if applicable)	100 patients
Follow up duration (if applicable)	6 months
Planned Study Period	2 years
Research Question/Aim(s)	Can you use MRI derived imaging parameters to predict the degree of side effects in patients receiving cranial radiotherapy as treatment for Glioblastoma Multiforme?

FUNDING AND SUPPORT IN KIND

FUNDER(S) (Names and contact details of ALL organisations providing funding and/or support in kind for this study)	FINANCIAL AND NON FINANCIAL SUPPORT GIVEN
Sussex Cancer Fund c/o [name] Royal Sussex County Hospital [name]	Funded the total cost of the study - £62,000

[figure not shown]

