3 THEORETICAL FRAMEWORK

Older patient with a GBM have an average prognosis of 3-6 months. Treatment options are universally palliative and should be aimed at improving or maintaining quality of life for the remainder of these patients' lives. Treatment decisions therefore need to be based around an informed conversation with the patient of the balance between survival benefit and side effect profile. Clinical trials have shown

efficacy of single agent radiotherapy or chemotherapy or short courses of concurrent chemoradiation. Molecular markers have been developed which can help guide decisions regarding the likely efficacy of chemotherapy however no such marker exist for decisions regarding radiotherapy.

Radiotherapy is an effective palliative treatment for GBMs and has been shown in clinical trials to maintain or improve health related quality of life. However outside of a clinical trial population, usual clinical practice reveals some patients in whom the side effect profile from cranial radiotherapy is intolerable and has a significant detrimental effect on patients' quality of life for their remaining short lifespan. The BRITER study aims to examine whether analysis of pre-treatment MRI scans in this cohort could help to predict who is more vulnerable to these side effects and therefore reveal a group of patients in whom single agent chemotherapy or best supportive care would be better treatment options.

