4 RESEARCH QUESTION/AIM(S)

4.1 Objectives

The BRITER study is being performed in patients aged 65 or over who have a new diagnosis of GBM. It tests the hypothesis that there is a relationship between 5 scores of a 'vulnerable' brain seen on pre-treatment MRI and a clinically significant change in patient quality of life, as defined by a 10 point change in the EORTC QLQ questionnaire from baseline to 8 weeks post treatment.

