4.2 Outcome

The primary outcome is the proportion of patients with a 10 point change in the EORTC QLQ C30 quality of life questionnaire (with the BN-20 brain and ELD14 elderly patient subsets of questions added) from baseline to 8 weeks.

The impact of side effects from cranial radiotherapy will also be assessed by the secondary outcomes of

- MOCA cognitive screening questionnaire
- use of corticosteroids
- degree of grade 3-5 CTCAE toxicity
- overall and progression free survival

5 STUDY DESIGN and METHODS of DATA COLLECTION AND DATA ANALYSIS

The BRITER study is an observational cohort study. Eligible patients will be identified during the multidisciplinary team meeting by the participants' usual care team. They will have previously been informed of their diagnosis and then will meet a member of the oncology team to discuss treatment options. Once it has been decided with them by their usual care team that they are to have radiotherapy treatment, they will be given a PIS. After the patient has had sufficient time to read the PIS and have any questions answered by a member of the study team they will be asked to complete a consent form. They will also undergo the baseline clinical assessments prior to starting any

radiotherapy treatment. This will be done during the outpatient appointment with the neuro oncology team.

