- 3D volumetric inversion recovery or MP-RAGE (additional sequence - to allow accurate quantification of cortical thickness/volumes using Freesurfer software in addition to scoring methods of atrophy, must be acquired at 1mm or below)
- Axial T2* gradient echo (4mm slice thickness)

The scan thickness and sequences performed may vary slightly between sites however prior to opening the sites will confirm they can produce the necessary sequences for [name] to produce 5 quantitative scores (tumour volume, contralateral hemispheric brain volume, contralateral cerebral hemisphere cortical thickness, microhaemorrhage score and white matter hyperintensity score) from the images which reflect the degree of potential vulnerability of the brain to the side effects of radiotherapy. These will then be analysed in relation to the clinical questionnaires, steroid usage and grade 3-5 CTCAE radiotherapy toxicity score using SPSS. Multivariable logistic regression models will be fitted to look for significant ($P<0.05$) relationships between the 10 point change in EORTC QLQ quality of life questionnaires and the MRI parameters. Exploratory statistical analysis of the relationships between the MRI parameters and the secondary endpoints will be performed although the study is not powered to detect statistically significant relationships between these.

The creation of the database and statistical analysis of the results will be performed by the CI with the help of a research assistant.

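### The study aims to predict side effects from MRI but plans only an association test at P<0.05, with no prespecified measure of predictive performance and no correction for overfitting

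*Combined protocol and SAP*

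**What the plan says.** The Study Summary puts prediction in the study title and asks: "Can you use MRI derived imaging parameters to predict the degree of side effects in patients receiving cranial radiotherapy". Section 2 hopes that knowing a patient's likely side effects would allow treatment to be tailored to the individual. Section 3 says that pre-treatment MRI "could help to predict who is more vulnerable to these side effects and therefore reveal a group of patients" for whom options other than radiotherapy might suit better.

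The formal hypothesis in section 4.1 is of another kind: "It tests the hypothesis that there is a relationship between 5 scores of a 'vulnerable' brain" and a clinically significant change in quality of life. Section 4.2 makes the outcome binary: "The primary outcome is the proportion of patients with a 10 point change in the EORTC QLQ C30 quality of life questionnaire", measured from baseline to 8 weeks.

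Section 5 gives the primary analysis in one sentence: "Multivariable logistic regression models will be fitted to look for significant ($P<0.05$) relationships" between that change and the MRI parameters, which are five scores. It adds that "Exploratory statistical analysis of the relationships between the MRI parameters and the secondary endpoints will be performed", without power for them.

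Section 7.2.1 derives 73 evaluable patients, inflates this to 91 for 20% attrition, notes that an event proportion of 5% would support only one variable, and sets a target of 100 so that five can be fitted. Nowhere do the documents mention AUC, sensitivity or specificity, calibration, internal or external validation, shrinkage, penalisation or multiplicity.

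**The concern.** A test of association and an assessment of prediction answer different questions. A score can reach P<0.05 and still separate patients poorly. A model fitted and judged on the same small group also looks better than it will in new patients. If the prediction question is answered from P-values, or from a fit statistic computed on the data that produced the model, the study could report useful prediction where there is little or none. The stake is the conclusion drawn in the final report, because section 3 hopes to identify a group of patients from it.

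**Working it through.** **Inputs from the plan.** 100 recruits and 20% attrition (section 7.2.1): 100 × 0.80 = 80 completers. Five scores and P<0.05 (section 5). The only event proportion stated is 5%; the SD is 22.1 (section 7.2.1).

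**The plan's own figure.** The 73 cannot be reproduced, because the hypothesised proportion is not given. With 5% as the alternative, the two-sided 90% power formula for one proportion gives 73 only for a null of about 0.36% or 16.9%. The attrition step does follow: 73 / 0.80 = 91.25, stated as 91. Neither step sizes a five-score model. At 5%, moving from 73 to 80 completers moves the expected events from 0.05 × 73 = 3.65 to 0.05 × 80 = 4.

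**Assumed event rate.** The true rate is unknown, so 5% to 50% is shown. The value 32.5% comes from assuming a normally distributed change with mean zero, SD 22.1, and only deterioration counted: Φ(−10/22.1) = 0.325, or 26 of 80. Counting change in either direction would double it to 65%.

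**A model with no predictive value.** Logistic fits with five normally distributed scores were simulated at n = 80, once with pairwise correlation 0.3 (one pair 0.6) and once with independent scores. The true AUC is 0.50. Ranges cover the different runs.

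| Event rate | Events | Events per score | Mean apparent AUC |
|---|---|---|---|
| 5% | 4 | 0.8 | 0.79–0.81 |
| 10% | 8 | 1.6 | 0.73–0.74 |
| 20% | 16 | 3.2 | 0.67 |
| 30–32.5% | 24–26 | 4.8–5.2 | 0.65 |
| 50% | 40 | 8.0 | 0.63–0.64 |

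Fits that could not be estimated were excluded from the independent-score runs.

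**The P<0.05 criterion under the same null.** Five independent tests give 1 − 0.95^5 = 22.6%. The simulations gave about 20% at 32.5–50% events (19% to 25% across runs at 30–50%). At 32.5%, the null studies with at least one P<0.05 had a mean apparent AUC of 0.70.

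**A model with some value.** With one true odds ratio of 1.8 per SD and 32.5% events, apparent AUC is 0.71 against 0.61 in new patients, with a median calibration slope of 0.48–0.49. At 15% (12 events) the figures are 0.74, 0.60 and 0.35. A slope near 0.5 means that predictions are about twice too extreme.

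**What P=0.05 means for separation.** For one normal score, the standardised difference that just reaches P=0.05 is d = 1.96 × √(1/n1 + 1/n0), and AUC = Φ(d/√2). With 16 and 64 patients, d = 0.548 and AUC = 0.65. With 40 and 40, d = 0.438 and AUC = 0.62.

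**Limits of the remedy.** Bootstrap correction brought the null AUC to about 0.54 at 30–50% events, but left it at 0.63 to 0.69 in two separate runs at 5%. The 95% half-width for an AUC of 0.70 at n = 80 (Hanley–McNeil) is about 0.12 at 50% events and 0.16 at 20%. For an expected shrinkage factor of 0.9 with five predictors, n = 5 / [(0.9 − 1) × ln(1 − R²/0.9)], where R² is the Cox–Snell value. At 50% events and an assumed Nagelkerke R² of 0.15, R² = 0.15 × 0.75 = 0.1125 and n = 375. Over 5% to 50% events the range is 375–891, or 215–524 if Nagelkerke R² is 0.25.

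**The case against.** The strongest reply is that section 4.1 states a hypothesis of a relationship, section 2 also speaks of correlation, and multivariable logistic regression addresses exactly that. This stands. A reader might infer that the study cannot answer its own question; the documents support that only for the prediction question in the Study Summary and section 3, not for the hypothesis in section 4.1.

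A reader might also infer that a P-value is the only planned output. That goes too far: section 5 plans exploratory analyses of the secondary endpoints, and nothing says that odds ratios and intervals will be withheld. None of those analyses measures prediction, however.

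A third tempting inference is that the result is meant to steer patients away from radiotherapy. Section 3 says only that the study examines whether MRI "could help to predict who is more vulnerable to these side effects", and sections 5 and 7.3.2 say that enrolment does not affect treatment. The plan proposes no AUC, risk score or cut-off, so an inflated AUC is a risk in later reporting and not a figure the plan has committed to.

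Overfitting is not wholly ignored either, since section 7.2.1 ties model size to the event proportion. Its remedy does not work on its own figures: about 4 events for five scores.

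Finally, optimism correction will not make 80 patients definitive. At 32.5% events the corrected AUC ranged over 0.44–0.65 with no effect and 0.51–0.75 with an odds ratio of 1.8, so the two overlap heavily. This is accepted. It argues for showing the interval and limiting the claim, not for relying on P<0.05.

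**Conclusion.** The concern holds in this form: the prediction wording goes beyond an analysis that tests association, and nothing prespecified would support a statement that MRI predicts decline in quality of life. The optimism is material at every event rate tried, adding about 0.13 to 0.15 to the AUC of a worthless model at 32.5–50% events (0.63–0.65 less 0.50) and about 0.30 at 5%. The sizes rest on assumptions: 80 completers, normal scores, the chosen correlations and effects, and an event rate the plan does not establish. The 32.5% is an illustration and not the plan's figure. The direction of the finding does not depend on these choices. It should be corrected before analysis; it does not invalidate the test of the section 4.1 hypothesis.

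**What to change.** Add to section 5, in words such as:

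> The five-score model will be reported with odds ratios per SD and 95% confidence intervals, and with the c-statistic and calibration slope corrected for optimism by bootstrap (at least 500 resamples, repeating every modelling step), with intervals. Any statement that MRI predicts decline in quality of life will rest on these and not on P<0.05 alone. If events are too few for five scores, a penalised (for example Firth or ridge) or reduced model will be used, no prediction claim will be made, and the result will be reported as exploratory association.

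Set the minimum number of events before outcomes are seen. The checks above show bootstrap correction behaving acceptably at about 24 to 40 events and failing at about 4; they do not locate the boundary between. State also that the interval will be wide (about ±0.12 to ±0.16 for an AUC of 0.70) and that external validation is needed before clinical use.

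The alternative is to reword the aim in the Study Summary and section 3 as exploratory association, in line with section 4.1.

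The cost is a few lines of text and a short script, with no new patients or data. The downside is a reported performance that is less favourable and visibly imprecise.

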7.2 Sampling

7.2.1 Size of sample

Sample size calculations have been performed assuming a clinically significant end point of a 10 point change (SD=22.1 taken from the EORTC website reference guide) in EORTC QLQ questionnaire score between baseline and 8 weeks. Estimated sample size for one-sample comparison of proportion to hypothesized value assuming a 2 sided alpha of 0.05 and power of 0.9 gives a sample of

73. However, allowing for 20% attrition in questionnaire completion, this results in a sample size of 91. With 73 patients at 8 weeks, we will have 90% power for 5% significance to detect 5% of patients achieving a 10 point change in QoL. However, this small a proportion will only allow us to fit one variable in the model. It has therefore been recommended by the statistical team to aim for a recruitment target of 100 patients in order to fit the 5 MRI variables to the model.

Patients who are enrolled within CTIMP studies will not be eligible to be recruited into the study as they would introduce too many unknown variables for adequate statistical analysis with a cohort of this size.

Previous work done by this study group has shown this is a feasible recruitment target over 2 years.

The study team will review recruitment at 9 months and if it has not reached 25% then they will explore ways to increase recruitment, including opening at other sites.

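### One hypothesis over five MRI scores has no decision rule or multiplicity control; if any score at P<0.05 counts, the false-positive rate is roughly 10–23%, not 5%

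*Combined protocol and SAP*

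**What the plan says.** Section 4.1 frames the study around one hypothesis: "there is a relationship between 5 scores of a 'vulnerable' brain seen on pre-treatment MRI and a clinically significant change in patient quality of life". Section 5 lists the "5 quantitative scores (tumour volume, contralateral hemispheric brain volume, contralateral cerebral hemisphere cortical thickness, microhaemorrhage score and white matter hyperintensity score" and then describes the main analysis: "Multivariable logistic regression models will be fitted to look for significant" relationships at P<0.05 between the binary quality-of-life outcome and the MRI parameters. That is the only threshold given.

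For the secondary endpoints Section 5 takes a different line: "Exploratory statistical analysis of the relationships between the MRI parameters and the secondary endpoints will be performed", with a note that the study is not powered for them. Only those analyses are called exploratory, so the five-score quality-of-life analysis is the one that tests the hypothesis.

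Section 7.2.1 uses a two-sided alpha of 0.05 and power of 0.9. It raises the target to 100 patients so that all five MRI variables can go into the model. No section gives a global test, a primary score, a multiplicity rule, the number of models to be fitted, or any correlation between the scores.

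**The concern.** The hypothesis is single, but the analysis looks for "significant ($P<0.05$) relationships between the 10 point change in EORTC QLQ quality of life questionnaires and the MRI parameters". A logistic model with five scores prints five P values. Unless the plan says beforehand what counts as support, a positive conclusion can rest on whichever of the five falls below 0.05.

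Two of the scores, "contralateral hemispheric brain volume, contralateral cerebral hemisphere cortical thickness", both bear on atrophy and may overlap. If they do, each separate P value can be non-significant even when atrophy matters. Reading coefficients one at a time can therefore produce false claims and can also miss a real shared effect.

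Section 3 intends the results to identify patients for whom treatment other than radiotherapy may be preferable. A marker that appeared by chance would be a poor basis for that.

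**Working it through.** **The plan's own figures.** The plan states no family-wise error rate, so there is none to reproduce. From Section 7.2.1, 73/0.8 = 91.25, which agrees with the stated 91. The 73 itself cannot be rebuilt because the null proportion is not given. Here 73 serves only as a model size, together with 100 × 0.8 = 80 (the recruitment target after 20% attrition).

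**Inputs from the documents.** Five scores; threshold 0.05, unadjusted; logistic model; 73 to 80 evaluable patients; 5% of patients with the 10-point change.

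**Assumptions, not in the documents.** Any score at P<0.05 counts as support; correlations between scores from 0 to 0.9; event proportions other than 5%.

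**Step 1: large-sample bounds.** Five independent tests: 1 − 0.95^5 = 0.226. The ceiling for five tests under any dependence is 5 × 0.05 = 0.25.

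**Step 2: effect of correlation** (1,000,000 draws of five Wald statistics under the global null, equal correlation between scores):

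| Correlation | One joint model | Five separate models |
|---|---|---|
| 0.2 | 22.2% | 21.8% |
| 0.5 | 21.6% | 18.3% |
| 0.7 | 21.4% | 14.8% |
| 0.9 | 21.2% | 10.2% |

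Correlation hardly changes the rate in a joint model. It lowers the rate in separate models, but still leaves it at about twice 5%.

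**Step 3: small-sample behaviour** (logistic regression under the global null, 2,000 runs per case, n = 73 and 80, three correlation patterns):

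| Event proportion | At least one P<0.05 | 5-df likelihood-ratio test | Fits failing |
|---|---|---|---|
| 20–50% | 18.4–23.2% | 5.8–7.7% | 0% |
| 5%, over all runs | 8.0–11.3% | 5.6–7.8% | 8–12% |
| 5%, converged fits only | 9.1–12.2% | 6.4–8.5% | – |

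The last row divides each case's rate by its share of converged fits; for example, 0.1125/(1 − 0.0795) = 0.122. The simulation standard error for a rate near 20% is √(0.2 × 0.8/2000) = 0.9 percentage points, so 18.4% and 19% are not distinguishable. At 10% events, a separate run gave about 17–21%.

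The lower rate at 5% events reflects sparse data: 73 × 0.05 = 3.65 and 80 × 0.05 = 4 events, too few for Wald tests to behave normally.

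**Step 4: overlap between volume and thickness.** The variance inflation for two scores with correlation r is 1/(1 − r²). At r = 0.5 it is 1/0.75 = 1.33, so standard errors rise by about 15% (√1.33 = 1.15). At r = 0.8 it is 1/0.36 = 2.78, and standard errors rise by about 67%.

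As an illustration, assume a true shared atrophy effect of 0.8 log-odds per SD of the composite, n = 80 and about 40% events. At r = 0.5, either atrophy score reached P<0.05 in 64% of runs and the 5-df test rejected in 71%. At r = 0.8 the figures were 33% and 71%.

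**The case against.** The strongest reply is that the protocol nowhere says one significant coefficient confirms the hypothesis. That is correct. A reader might infer a written any-hit rule from Section 5, but the text would also accommodate an overall test of the five scores. The gap is therefore an unspecified rule, which leaves the choice open until the results are seen.

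A reader might also take 23% as the error rate of this study. The documents do not support a flat figure. It needs an any-hit rule, independent or jointly modelled scores, and enough events. At the plan's own 5% proportion the rate is about half that, and the gain from a joint test is correspondingly small. However, Section 7.2.1 itself says so small a proportion supports only one variable, so a five-score model presupposes more events.

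It is tempting to say that overlap makes the named atrophy marker arbitrary. At an assumed correlation of 0.5, a 15% rise in standard errors does not justify that. At 0.8 the problem would be serious, but the documents give no value. Overlap affects power and interpretation; it does not drive the false-positive rate.

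Finally, this is an observational cohort that does not alter participants' treatment, and showing all five coefficients with intervals would let readers judge. That has weight, but Section 4.1 declares a hypothesis test and Section 5 reserves the exploratory label for the secondary endpoints.

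**Conclusion.** The concern holds in conditional form. The plan tests one hypothesis over five scores with no global test, lead score or multiplicity control. If any score at P<0.05 is read as support, the false-positive rate is roughly 10–23% against a nominal 5%:

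- about 19–23% in one joint model with 20% or more events;
- about 10–12% among converged fits at the 5% proportion;
- about 10–22% in separate models, depending on an unstated correlation.

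The error exceeds 5% in every scenario examined. These ranges cover one set of five tests. Neither the number of models nor the questionnaire scale that carries the 10-point change is fixed, so further tests could raise the rate. The P values for hemispheric volume and cortical thickness should be read with caution. This is a cheap improvement that should be made; it does not invalidate the study.

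**What to change.** Add to Section 5 that the primary test is a single likelihood-ratio test on 5 degrees of freedom, at the 5% level. It compares the logistic model for the binary 10-point change containing all five MRI scores with the same model without them. The test is non-directional, which agrees with the two-sided alpha in Section 7.2.1. State that individual coefficients are reported with confidence intervals as descriptive results, or are Holm-adjusted if a single marker is to be claimed. An F test is not a substitute, because it belongs to a continuous outcome that the plan does not use.

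The cost is a sentence or two of wording and one extra line of SPSS output, with no more patients, scans or data. There are three limits:

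- One unadjusted P<0.05 would no longer confirm the hypothesis.
- The joint test does not say which score matters, so it deals with the volume and thickness overlap for the overall claim only.
- Its simulated error is still slightly above nominal, at about 5–8%, and it does not make a five-score model dependable with about four events.
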